Study Design: This is a Phase 1/2a, open-label study of relatlimab administered as monotherapy or in combination with nivolumab to subjects with relapsed or refractory B-cell malignancies. The study will be conducted in 4 parts. Part A consists of a 3 + 3 + 3 dose escalation design in subjects with relapsed or refractory Chronic Lymphocytic Leukemia (CLL), HL, NHL, and multiple myeloma (MM) with relatlimab administered as monotherapy. Part B consists of cohort expansion in [REDACTED] disease-restricted populations of [REDACTED] to [REDACTED] subjects each with relatlimab administered as monotherapy. Part C consists of a 3+3+3 dose escalation design in subjects with advanced HL and DLBCL with relatlimab administered in combination with nivolumab. Part D consists of cohort expansion in three disease restricted populations of [REDACTED] to [REDACTED] subjects each with relatlimab administered in combination with nivolumab ([Figure 1](#)).

Figure 1: Study Design Schematic

* In Part A, and selected cohort in Part D (ie, Hodgkin Lymphoma PD-1/PD-L1 naïve cohort), subjects will be naïve to immune cell-modulating antibody regimens (ICMARs), such as but not limited to anti PD-1, anti PD-L1, anti PD-L2, anti CTLA-4, anti-KIR, and/or anti-OX40 antibodies. Prior anti-CD20, alemtuzumab, and/or anti-CD30 antibody therapy are allowed.

**In Part B, Part C, and selected cohorts in Part D (ie, Hodgkin Lymphoma anti-PD-1/PD-L1 resistant/failure cohort and Diffuse Large B-Cell Lymphoma cohort), subjects will be naïve to immune cell-modulating antibody regimens (ICMARs), such as, but not limited to anti CTLA-4, anti PD-L2, anti-KIR, and/or anti-OX40 antibodies. Prior anti-PD-1, anti-PD-L1, anti CD137, anti-CD20, alemtuzumab, and/or anti-CD30 antibody therapy are allowed.

Subjects will complete up to 4 periods of the study: Screening (up to 28 days), Treatment (up to a maximum of [redacted] -week cycles of study therapy), Clinical Follow-up (135 days following the last dose of study drug) and **Survival Follow-up** (up to [redacted] years following the first dose of study drug). Women of childbearing potential (WOCBP) will have additional follow-up assessments through Day 165 for home pregnancy tests. An independent period, Re-challenge, may be conducted in selected cases at progression.

[figure not shown]

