The **Treatment Period** consists of up to twelve 8-week treatment cycles. Each treatment cycle comprises [redacted] doses of relatlimab administered on Days [redacted]. Subjects will be allowed to continue study therapy until the first occurrence of either: (1) meeting criteria for discontinuation as described in [Section 4.3.5](#), (2) completion of the maximum number of twelve 8-week cycles, (3) confirmed progressive disease (PD), or (4) clinical deterioration. Subjects who discontinue treatment will enter a 135-day **Clinical Follow-up** period. After completion of the **Clinical Follow-up period**, HL patients in Parts C and D will enter the **Survival Follow-up period**. During this period, clinic visits or telephone contact every 12 weeks will be performed to assess survival status. For participants who discontinue study treatment prior to disease progression, diagnostic imaging will be obtained every 6 months after the first clinical

follow-up in year 1 and in year 2, and annually thereafter for a total of 5 years maximum (since the first dose of the study drug) until disease progression. **Re-challenge** may be conducted in selected cases at progression.

If subjects progress during the Clinical Follow-Up period or the Survival Follow-Up period, they could further receive therapy with relatlimab alone or in combination with nivolumab (Re-challenge period) as long as the risk:benefit ratio is considered favorable by the Investigator and the Medical Monitor and eligibility criteria is met (Section 3.3). The original dose and schedule and protocol rules would apply accordingly. Thus, subjects could receive therapy for up to 12 additional eight-week cycles. Subjects will not be re-challenged a second time. Collection of archival tissue (baseline) and tumor biopsies (baseline and on-treatment) will be optional for subjects enrolled for re-challenge. PK and biomarker monitoring will be limited (Sections 5.5 and 5.7).

A study schematic is shown in Figure 2.

Figure 2: Study Schematic for Parts A,1 B, C, and D

¹ Part A DLT period: 8 weeks.

² Treatment beyond progression may be considered in selected subjects as described in Protocol Section 4.3.4.

³ WOCBP will have additional follow-up assessments through Day 165 for home pregnancy tests.

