If subjects progress during the clinical follow-up period or the survival follow-up period, they could further receive therapy with relatlimab alone or in combination with nivolumab (Re-challenge) as long as the risk:benefit ratio is considered favorable by the Investigator and the Medical Monitor and the following eligibility criteria is met: 1) Subject has confirmed disease progression 2) Subject has not experienced relatlimab related adverse events leading to permanent discontinuation. The original dose and schedule of therapy and protocol rules will apply. Thus subjects could receive therapy for up to 6 additional eight-week cycles.

Subjects who are re-challenged and who subsequently have an objective response will not be included in the primary analysis of efficacy. Responses to re-challenge will be evaluated in a separate analysis. Subjects will not be re-challenged a second time.

Dose-Limiting Toxicities:

For the purpose of guiding decisions regarding dose escalation in Part A, (DLT) will be determined based on the incidence, intensity, and duration of AEs that are related to study drug and that occur within 8 weeks of initiation of study drug (ie, the DLT evaluation interval which begins on the first day of treatment and ends on Day 56 of the first cycle).

For the purpose of guiding decision in combination dose escalation in Part C, (DLT) will be determined based on the incidence, intensity, and duration of AEs that are related to study drug and that occur within 4 weeks of initiation of study drug (ie, the DLT evaluation interval which begins on the first day of treatment and ends on Day 29 of the first cycle).

Adverse events will be graded according to the National Cancer Institute (NCI) Common Terminology Criteria for Adverse Events version 4.0 (CTCAE v4.0). For the purpose of subject management, any AE that meets DLT criteria, regardless of the cycle in which it occurs, will lead to dose interruption.

Dose escalation will be based on the number of DLTs experienced during the DLT evaluation interval as determined by the Medical Monitor and Investigators.

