The **Treatment Period** consists of up to twelve 8-week treatment cycles. Each treatment cycle comprises 4 doses of relatlimab administered on Days [REDACTED]. Subjects will be allowed to continue study therapy until the first occurrence of either: (1) meeting criteria for discontinuation as described in [Section 4.3.5](#), (2) completion of the maximum number of twelve [REDACTED] cycles, (3) confirmed progressive disease (PD), or (4) clinical deterioration. Subjects who discontinue treatment will enter a 135-day **Clinical Follow-Up Period**. After completion of the **Clinical Follow-Up period**, HL patients in Parts C and D will enter the **Survival Follow-Up period**. For participants who discontinue study treatment prior to disease progression, diagnostic imaging will be obtained every 6 months after the first clinical follow-up in year 1 and in year 2, and annually thereafter for a total of 5 years maximum (since the first dose of the study drug) until disease progression. **Re-Challenge** may be conducted in selected cases at progression.

If subjects progress during the clinical follow-up period or the survival follow-up period, they could further receive therapy with relatlimab alone or in combination with nivolumab (Re-Challenge period) as long as the risk:benefit ratio is considered favorable by the Investigator and the Medical Monitor and eligibility criteria is met ([Section 3.3](#)). The original dose and schedule and protocol rules would apply accordingly. Thus, subjects could receive therapy for up to [REDACTED] additional eight-week cycles. Subjects will not be re-challenged a second time. Collection of archival tissue (baseline) and tumor biopsies (baseline and on-treatment) will be optional for subjects enrolled for re-challenge. PK and biomarker monitoring will be limited ([Sections 5.5](#) and [5.7](#)).

A study schematic is shown in Figure 3.1-2.

Figure 3.1-2: Study Schematic for Parts A,¹ B, C, and D

- 1 Part A DLT period: 8 weeks
- 2 Treatment beyond progression may be considered in selected subjects as described in Protocol [Section 4.3.4](#)
- 3 WOCBP will have additional follow-up assessments through Day 165 for home pregnancy tests

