3.1.5 Re-challenge in Dose Escalation (Part C) and Cohort Expansion (Part D)

If subjects progress during the clinical follow-up period or the survival follow-up period, they could further receive therapy with relatlimab alone or in combination therapy (Re-challenge) as long as the risk:benefit ratio is considered favorable by the Investigator and the Medical Monitor and the following eligibility criteria are met: 1) Subject has confirmed disease progression; 2) Subject has not experienced relatlimab related adverse events leading to permanent discontinuation. The original dose and schedule of therapy and protocol rules will apply. Thus subjects could receive therapy for up to [REDACTED] additional eight-week cycles. Subjects who are re-challenged and who subsequently have an objective response will not be included in the primary analysis of efficacy. Responses to re-challenge will be evaluated in a separate analysis. Subjects will not be re-challenged a second time.

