5.5.1 Pharmacokinetics - Collection and Processing

Pharmacokinetic blood samples will be drawn from study subjects receiving relatlimab as monotherapy or in combination with nivolumab at the time points indicated in Table 5.5.1-1 and Table 5.5.1-2. All time points are relative to the start of study drug administration. All samples collected pre-dose should be taken within 30 minutes before the start of dose administration. End-of-infusion samples should be taken just prior to the end of infusion (preferably within 2 minutes) from the contralateral arm (ie, the arm not used for the infusion). On-treatment samples are intended to be drawn relative to actual dosing days. If a dose occurs on a different day within the cycle due to minor schedule adjustments or dose delays, PK samples should be adjusted accordingly. Further details of sample collection, processing, and shipment will be provided in the Laboratory Procedures Manual.

Table 5.5.1-1: PK and ADA Sampling Schedule for Relatlimab and Nivolumab in all Subjects in Part A, B, C and ██████ Subjects in Part D and for Cohorts with Re-Challenge

Study Day of Sample Collection (1 Cycle = 56 Days [8 Weeks])	Event	Time (Relative to Start of Infusion) Hour: Min	Relatlimab PK Sample (All Subjects)	Relatlimab ADA Sample (All Subjects)	Nivolumab PK Sample (Part C & D Only)	Nivolumab ADA Sample (Part C & D Only)
Cycle 1						
1	predose ^a	00:00	X	X	X	X
1	EOI ^b	01:00	X		X	
1		04:00	X			
2		24:00	X			
3-5		48:00 - 96:00 ^c	X			
7-9		144:00 - 192:00 ^c	X			
15	predose ^a	00:00	X	X	X	X
29	predose ^a	00:00	X	X	X	X
43	predose ^a	00:00	X		X	
Cycle 2						
1	predose ^a	00:00	X	X	X	X
1	EOI ^b	01:00	X		X	
15	predose ^a	00:00	X		X	
29	predose ^a	00:00	X		X	
Cycle 3						
1	predose ^a	00:00	X	X	X	X
1	EOI ^b	01:00	X		X	

Table 5.5.1-1: PK and ADA Sampling Schedule for Relatlimab and Nivolumab in all Subjects in Part A, B, C and ██████ Subjects in Part D and for Cohorts with Re-Challenge

Study Day of Sample Collection (1 Cycle = 56 Days [8 Weeks])	Event	Time (Relative to Start of Infusion) Hour: Min	Relatlimab PK Sample (All Subjects)	Relatlimab ADA Sample (All Subjects)	Nivolumab PK Sample (Part C & D Only)	Nivolumab ADA Sample (Part C & D Only)
1		04:00	X			
2		24:00	X			
3-5		48:00 - 96:00 ^b	X			
7-9		144:00 - 192:00 ^b	X			
15	predose ^a	00:00	X		X	
Subsequent Odd # Treatment Cycles						
1	predose ^a	00:00	X	X	X	X
Follow-up Period						
FU2 ^d	FU2		X	X	X	X
FU3 ^d	FU3		X	X	X	X

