6.2.1 Non-serious Adverse Event Collection and Reporting

The collection of non-serious AE information should begin at initiation of study drug and for 135 days after discontinuation of dosing or until starting a new anti-neoplastic treatment (whichever occurs first). Non-serious AE information should also be collected from the start of a placebo lead-in period or other observational period intended to establish a baseline status for the subjects.

Non-serious AEs should be followed to resolution or stabilization, or reported as SAEs if they become serious (see [Section 6.1.1](#)). Follow-up is also required for non-serious AEs that cause interruption or discontinuation of study drug and for those present at the end of study treatment as appropriate. All identified non-serious AEs must be recorded and described on the non-serious AE page of the CRF (paper or electronic).

Completion of supplemental CRFs may be requested for AEs and/or laboratory abnormalities that are reported/identified during the course of the study.

Immune-mediated adverse events are AEs consistent with an immune-mediated mechanism or immune-mediated component for which non-inflammatory etiologies (eg, infection or tumor progression) have been ruled out. IMAEs can include events with an alternate etiology which were

exacerbated by the induction of autoimmunity. Information supporting the assessment will be collected on the subject's case report form.

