	Treatment during the Re-challenge period was changed from 12 additional eight-week cycles to 6 additional eight-week cycles.	
Decreasing re-challenge period ensures the study data can be concluded in a reasonable time period.
 
Based on previous study experience, the re-challenge data is not expected to have significant impact on study conclusion.

Section 3.3.1 Part C Dose Escalation Combination Therapy, Section 3.3.1 Inclusion Criteria 2 e) ii	Allowed patients progressed within 3 months of previous anti-PD1 or anti-PD-L1 treatment.	Progression within 3 months of previous anti-PD1/PD-L1 is allowed according to the MOA.
Section 3.3.1: Inclusion Criteria 1 b) iv)	Changed the requirement for “the first 6 subjects” to “All subjects” in Part D must consent to allow on-treatment biopsy. Additionally if a fresh pre-treatment tumor biopsy was not medically feasible and enrollment was approved by the Medical Monitor with an archival tumor sample, the on-	
The requirement for All subjects to consent for on-treatment biopsy was changed which will allow a more comprehensive investigation of markers associated to response and mechanisms of resistance.
 
With the BMS Medical Monitor approval of

Summary of key changes of Revised Protocol 07		
Section Number & Title	Description of Change	Brief Rationale
	treatment tumor biopsy will not be required.	enrollment without a fresh pre-treatment biopsy, the on-treatment biopsy is also not required.
Section 3.3.2: Exclusion Criteria	Exclusion Criteria 2h) vii) details of Cardiac Troponin test results were clarified. 2J i), ii), iii) was revised to clarify hepatitis exclusion criteria.	The exclusion criterion text for Troponin and cardiac evaluation is revised to align with the most recent program requirements based on updated safety information. Exclusion criteria for hepatitis was updated to align with the standard program requirements
Section 3.4.2.2 Imaging Restrictions and Precautions	Added Imaging Restrictions and Precautions	Imaging restrictions and precautions were added to the study to provide guidance when using contrast.
Section 4.3.2 Dose Delay Criteria	Updated the dose delay criteria. Removed Grade 3 skin and added Grade 1 myocarditis and troponin elevations. Also added text defining delayed doses, maximum delays, and subsequent dosing.	To align with most recent program requirements based on updated safety information.

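### Re-challenge length, stopping after a Grade 3 infusion reaction, and attenuated-virus vaccines are each stated in a stricter and a looser form

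*Combined protocol and SAP*

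**What the plan says.** **Re-challenge.** In the Synopsis, the Study Design text on subjects who progress during clinical or survival follow-up states: "Thus, subjects could receive therapy for up to 12 additional eight-week cycles". Later in the Synopsis, under the re-challenge heading for dose escalation and cohort expansion, the rule for the same subjects reads: "Thus subjects could receive therapy for up to 6 additional eight-week cycles". The matching figures in Sections 3.1 and 3.1.5 are redacted. The Revised Protocol 07 entry in Appendix 8 records: "Treatment during the Re-challenge period was changed from 12 additional eight-week cycles to 6 additional eight-week cycles".

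**Grade 3 infusion reaction.** Section 3.4.4, under Grade 3 or 4 symptoms, directs permanent discontinuation of study drug and sets no time condition. Section 4.3.5 exempts infusion reactions from its general Grade 3 rule, then requires permanent discontinuation for a Grade 3 infusion reaction only if it has not come back to Grade 1 within 6 hours.

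**Vaccines.** Section 3.4.1 lists live / attenuated vaccines as prohibited during treatment and for 100 days after the last dose. The exclusion criteria in Section 3.3.2 also treat live / attenuated virus as one class. Section 3.4.2.1 says that vaccines with attenuated or inactivated virus may be allowed when clinically indicated, subject to prior documented discussion with the Medical Monitor. Its closing sentence bars live virus only.

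**The concern.** All three mismatches lie between parts of the current text, so they do not depend on comparing the protocol with a superseded version. They concern dosing and subject protection: how long a subject may be re-treated, when study drug must stop, and which vaccines may be given to someone on checkpoint inhibitors. A site that reads only the looser place would act in a way the stricter place does not allow.

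The infusion-reaction rule has two further consequences. Discontinuation because of an AE is a named component of the primary safety endpoint (Section 8.3.1), so the same reaction could be counted at one site and not at another. Re-challenge is also closed to subjects who stopped permanently for a relatlimab-related AE (Synopsis and Section 3.1.5), so the choice of rule can decide whether a subject may be re-challenged later.

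**Working it through.** The protocol gives no figure to reproduce here. The check sets the rules side by side, with simple arithmetic for the first.

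**1. Re-challenge ceiling.** Inputs: 12 or 6 cycles (the two Synopsis paragraphs), 8 weeks per cycle (same paragraphs), and 4 doses per cycle from Section 3.1: "Each treatment cycle comprises 4 doses of relatlimab administered on Days".

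- Weeks = cycles × 8: 12 × 8 = 96; 6 × 8 = 48.
- Relatlimab doses = cycles × 4: 12 × 4 = 48; 6 × 4 = 24.
- With the initial 12 cycles (96 weeks), maximum total therapy is 96 + 96 = 192 weeks or 96 + 48 = 144 weeks.

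Both figures are upper limits. Giving 6 cycles or fewer meets both paragraphs; giving 7 to 12 meets only the first. Appendix 8 is used here only as evidence of intent, and it points to 6.

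**2. Grade 3 infusion reaction.**

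- Grade 4: the specific 6-hour condition is confined to Grade 3, so Grade 4 is not in dispute.
- Grade 3, not back to Grade 1 within 6 hours: stop under both sections.
- Grade 3 bronchospasm or hypersensitivity: stop under both, because Section 4.3.5 requires it whatever the duration.
- Any other Grade 3 reaction back to Grade 1 within 6 hours: stop under Section 3.4.4; stopping not required by the infusion-reaction criterion in Section 4.3.5.

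Only the last group is disputed. It shrinks further because Section 4.3.5 also stops any subject whom the Investigator judges to be at substantial risk from continued dosing. Section 4.3.5 says when stopping is required and never requires dosing to continue, so stopping in every Grade 3 case is consistent with both sections. The size of the group is unknown: Section 1.4.1.7 reports combination-therapy infusion reactions of Grade 3 or lower with the count redacted, which leaves open whether any were Grade 3.

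**3. Vaccines.**

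- Live virus: barred in Sections 3.4.1 and 3.4.2.1.
- Inactivated virus: not barred in Section 3.4.1; may be allowed under Section 3.4.2.1.
- Attenuated virus: barred in Section 3.4.1; may be allowed under Section 3.4.2.1.

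Only the third line conflicts. Withholding an attenuated vaccine satisfies both sections. Appendix 8 records that the prohibition in Section 3.4.1 was added in Revised Protocol 08, which suggests that Section 3.4.2.1 was not brought into line.

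**The case against.** The strongest reply is that nothing here is impossible to obey. A reader might infer that sites cannot comply with both versions. The documents do not support that: two ceilings, a list of mandatory stopping reasons and a conditional permission can all be met by taking the stricter text. That part of the objection stands. What remains is that the looser text is also in force, and nothing tells a site which one governs.

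A reader might also infer that the re-challenge discrepancy distorts the primary safety endpoint. AE collection runs from the start of study drug to 135 days after dosing ends (Section 6.2.1), so a higher ceiling permits a longer window. The re-challenge text carves out efficacy ("Subjects who are re-challenged and who subsequently have an objective response will not be included in the primary analysis of efficacy"), and Section 8.3.1 analyses every treated subject for safety. But the Synopsis calls re-challenge "An independent period, Re-challenge, may be conducted in selected cases at progression", and no section says whether its AEs are pooled with those of first treatment. The effect would also need a subject who stays on re-challenge beyond 48 weeks. The same Appendix 8 row that gives the figure of 6 says re-challenge data are not expected to matter much to the study's conclusions. No effect on a reported rate is shown. The vaccine rule has no demonstrated link to the endpoint either.

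Three points narrow the infusion-reaction item without removing it. Section 3.4.4 presents its steps as recommendations that local standards may modify. It describes Grade 3 as prolonged, recurrent or needing hospital care, which leaves fewer reactions that resolve within 6 hours. The end of Section 4.3.5 allows restarting therapy case by case. Even so, the stopping instruction in Section 3.4.4 is worded without condition, and under it the 6-hour criterion has no function.

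Finally, Investigator and Medical Monitor agreement governs who is re-challenged but does not set the number of cycles. Medical Monitor discussion makes an improper vaccination less likely but does not reconcile the two sections.

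**Conclusion.** The point holds as a minor safety and conduct correction covering three rules, each stated in a stricter and a looser form.

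- **Re-challenge:** the two ceilings differ two-fold, 96 weeks and 48 doses against 48 weeks and 24 doses. These are maxima, not expected exposure, and assume 4 doses in every cycle. The conflict is shown only within the Synopsis, because the figures in Sections 3.1 and 3.1.5 are redacted.
- **Infusion reaction:** the dispute is confined to Grade 3 reactions that resolve within 6 hours and are not bronchospasm or hypersensitivity. For these, the choice of rule can change the count of AEs leading to discontinuation and, if the reaction is relatlimab-related, eligibility for re-challenge.
- **Vaccines:** the dispute is confined to attenuated-virus products.

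No effect on the primary endpoint is shown for the first and third items. No sample size, decision rule or planned analysis changes. How many subjects were affected, if any, cannot be derived from the documents.

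**What to change.** - **Re-challenge:** in the Study Design part of the Synopsis, change 12 additional cycles to 6, and confirm that the redacted figures in Sections 3.1 and 3.1.5 also read 6.
- **Infusion reaction:** the clinical team should choose one rule. Either keep the 6-hour condition in Section 4.3.5 and have Section 3.4.4 refer to it for Grade 3, or stop for every Grade 3 reaction and remove the condition from Section 4.3.5. Whichever section does not hold the rule should cross-reference the one that does. No extra listing is needed, since Section 8.4.3 already provides for AEs to be listed.
- **Vaccines:** in Section 3.4.2.1, delete *attenuated or* from the permissive sentence and make the closing prohibition cover live or attenuated virus.

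The cost is three short wording changes in a clarification letter or the next amendment. The second needs a clinical decision.
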